#### N. Ethical Aspects of RCTs

**a. Participant consent.** At the beginning of the training module in MyLearning, PCCs will be given the consent form outlining the project, potential risks and benefits, and privacy and confidentiality protections. Participants will have the opportunity to review

the consent form and provide consent by clicking a button: "I have read the above consent form and I agree to participate." If participants have questions about consent or the project, they will be directed to contact the study principal investigator or project manager by email or phone.

# O. RCT Management

- a. Registering the trial. This study will comply with the NIH Data Sharing Policy and Policy on the Dissemination of NIH-Funded Clinical Trial Information and the Clinical Trials Registration and Results Information Submission rule. As such, this trial will be registered at ClinicalTrials.gov, and results information from this trial will be submitted to ClinicalTrials.gov. In addition, every attempt will be made to publish results in peer-reviewed journals.
- b. Research governance and good clinical practice. Study staff are required to complete institutionally required training per their research site, IRB(s), and authorities with regulatory oversight. Training will include Human Subject Protection (HSP) and Good Clinical Practice (GCP), as well as protocol-specific training.

# P. Reporting, Dissemination and Notification of results

- **a. Trial Registration.** In keeping with NIH policy, this trial will be registered at ClinicalTrials.gov, and results information from this trial will be submitted to ClinicalTrials.gov.
- **b. Publication policy.** We will publish results in peer-reviewed journals. The planning, preparation and submission of publications will follow the policies of the Publications Committee of the CTN.
- c. Disseminating results to the public. As a result of our previous and ongoing OUD and mental health research, we have established communication channels with key stakeholders in our health system, as well as with external stakeholders, including the NIDA CTN, the Mental Health Research Network, the Midwest Research Network, and the Health Care Systems Research Network. We anticipate that our findings will be of significant interest to these groups, and we will disseminate our findings, methods and resources. We will share our findings immediately through presentations at local and national meetings. We will publish our findings in peer-reviewed journals and communicate our findings to public media outlets.
- d. Data Sharing. The study investigators will share a limited de-identified data set used for primary outcome analysis with NIDA for NIDA's Data Share website. The CTN DSC can assist the study investigators with providing the data set to the designated party to ensure de-identification, and for posting, storing, and archiving on NIDA's Data Share website. Data Share is an online repository of data from studies funded by the NIDA and is located at: https://datashare.nida.nih.gov/. In addition, we have partnered with [name], an assistant professor in psychiatry at the University of Illinois at Chicago (UIC), who is interested in stigma of people with substance use disorders. We are finalizing a data transfer agreement with UIC, and [name] will be conducting secondary analyses on our data based on her interest in understanding how race/ethnicity interacts with stigma to affect willingness to treat people with OUD.

# **Appendix D: Immediate Post Training Survey**

#### **EXPERIENCE WITH THE OPIOID WIZARD TRAINING**

1. This training on Opioid Wizard will help me improve my practice.

Strongly disagree	Disagree	Neutral	Agree	Strongly Agree
1	2	3	4	5

2. This training on Opioid Wizard helped me better understand how to use it.

Γ	Strongly				
	disagree	Disagree	Neutral	Agree	Strongly Agree
Г	1	2	3	4	5

3. I found this training on Opioid Wizard easy to understand.

Strongly			_	
disagree	Disagree	Neutral	Agree	Strongly Agree
1	2	3	4	5

4. How likely are you to use Opioid Wizard during clinic visits with patients who are thought to be at high risk for opioid use disorder or overdose?

Strongly			_	
disagree	Disagree	Neutral	Agree	Strongly Agree
1	2	3	4	5

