# c. Secondary Outcome Measures

- i. Waivered PCC prescribing and referral behavior. As an exploratory outcome, we will gather the rate of MOUD, naloxone, and opioid prescriptions and referrals to waivered clinicians (primary care and specialty addiction medicine) among eligible patients in the 12 months prior to the study and during the 6-month follow-up period to determine whether the stigma reduction and/or control training affected change in prescribing behavior.
- ii. PCC waiver status. In addition to intentions to get waivered, change in waiver status will be collected as an exploratory outcome. A list of waivered PCCs will be pulled from HP administrative data to determine if additional PCCs became waivered during the follow-up period.
- iii. *PCC willingness to work with people with OUD.* PCCs will report on their willingness to work with people with OUD using 3 items adapted from the Drug Problems Perceptions Questionnaire.  PCCs will respond to each item using a 5-point Likert-type scale ranging from 1 (*strongly disagree*) to 5 (*strongly agree*). One item is reverse scored ("I would enjoy my job more if I could stop working with patients with opioid use disorder") and the items will be averaged for a total score, with higher scores corresponding to greater willingness to work with people with OUD.
- iv. PCC opioid treatment outcome expectancies. Treatment outcome expectancies will be assessed using two items developed for this study. First, PCCs will rate the extent to which they believe available treatments are effective for treating OUD on a 4-point Likert-type scale ranging from 1 (not at all effective) to 4 (very effective). The second item will ask PCCs to rate the extent they believe patients will comply with those treatments on a 4-point Likert-type scale ranging from 1 (not at all likely) to 4 (very likely). Items will be analysed separately.
- v. PCC perceptions of the training and the Opioid Wizard tool. In the initial survey, PCCs will provide feedback on the training in four questions, including their perception of the usefulness and ease of use of the training and their intentions to use the Opioid Wizard tool. At the 3-month follow-up survey, these questions will be replaced with items specifically about Opioid Wizard, not the training, to assess likelihood of recommending Opioid Wizard to colleagues, frequency of using Opioid Wizard, Opioid Wizard ease of use, and intention to use Opioid Wizard in the future.

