# Appendix E: 3-month Follow-up Survey

#### **EXPERIENCE WITH OPIOID WIZARD**

- 1. Have you ever used Opioid Wizard?
  - No
  - Yes

If NO, SKIP to question 5.

2. How likely are you to recommend Opioid Wizard to a colleague?

	J			
	Somewhat		Moderately	
Not at all likely	Not very likely	likely	likely	Very likely
1	2	3	4	5

- 3. How often do you use Opioid Wizard when a patient has been identified as being at risk for OUD or overdose within the EHR by the Opioid Wizard?
  - Not applicable; I have not had patients identified as at risk for OUD or overdose
  - None of the time
  - Some of the time
  - Most of the time
  - Every time

4. Opioid Wizard makes it easier to discuss OUD treatment options with patients.

Strongly	Ċ	NI. C. I	A	01
disagree	Disagree	Neutral	Agree	Strongly Agree
1	2	3	4	5

5. When alerted to patients at increased risk of OUD or overdose, how likely are you to use Opioid Wizard during clinic visits in the future?

I definitely will				
not	I likely will not	Unsure	I likely will	I definitely will
1	2	3	4	5

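### The immediate item on intention to use Opioid Wizard has answer labels that do not fit its question, and the 3-month ease-of-use item asks about something else (minor)

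*Combined protocol and SAP*

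**What the plan says.** Section H.c.v (Secondary Outcome Measures) describes a perception outcome at two times. In the initial survey, four questions are to cover "perception of the usefulness and ease of use of the training and their intentions to use the Opioid Wizard tool". At 3 months these give way to items on the tool itself: likelihood of recommending it, and "frequency of using Opioid Wizard, Opioid Wizard ease of use, and intention to use Opioid Wizard in the future". The section states no response scale and no scoring for any of these items.

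The items are printed in the appendices. In Appendix D, items 1 to 3 are statements about the training, such as "I found this training on Opioid Wizard easy to understand". Item 4 is a question: "How likely are you to use Opioid Wizard during clinic visits with patients who are thought to be at high risk". All four carry the same five labels, ending at "Strongly Agree".

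In Appendix E, item 4 reads "Opioid Wizard makes it easier to discuss OUD treatment options with patients", with agree-disagree labels. Item 5 asks, for occasions when the clinician has been alerted, "how likely are you to use Opioid Wizard during clinic visits in the future". Its five labels run from *I definitely will not* to *I definitely will*.

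**The concern.** Two items do not line up with what they are meant to record.

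First, a how-likely question cannot be answered by agreeing or disagreeing. A clinician who ticks *Agree* may mean that use is likely, or may be endorsing the idea of using the tool, and the analyst cannot tell which. This is the only immediate measure of intention to use Opioid Wizard. The same intention is asked at 3 months under different labels, so the two waves are not on one scale.

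Second, a result reported as ease of use at 3 months would rest on an item about a conversation with a patient. A clinician could find the tool awkward to operate and still agree that it helps in discussing treatment, or the reverse.

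At stake is how a listed secondary outcome is interpreted and labelled when it is reported.

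**Working it through.** The documents give no figure for these items, so there is nothing to recompute. The check is to match each construct named in Section H.c.v to the printed item, and each stem to its labels.

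**Immediate survey (Appendix D)**

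| Construct in H.c.v | Item | Stem | Labels | Fit |
|---|---|---|---|---|
| Usefulness of the training | 1, 2 | Statements | Agree-disagree | Yes |
| Ease of use of the training | 3 | Statement | Agree-disagree | Yes |
| Intention to use the tool | 4 | How-likely question | Agree-disagree | No |

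The mismatch does not look like an artefact of text extraction. The label row under item 4 is complete, numbered 1 to 5, and the same as for the three statements above it. Suitable labels stand elsewhere in the same instruments: Appendix D item 5a and Appendix E item 5 use *I definitely will not* to *I definitely will*, and Appendix E item 2 uses a likelihood scale.

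**3-month survey (Appendix E)**

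| Construct in H.c.v | Item | What the item asks | Fit |
|---|---|---|---|
| Recommending the tool | 2 | Likelihood of recommending it | Direct |
| Frequency of use | 3 | How often it is used for flagged patients | Direct |
| Ease of use | 4 | Whether it makes discussing treatment options easier | Approximate at best |
| Intention to use | 5 | Likelihood of future use when alerted | Direct |

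Three of the four constructs have a direct item. Four constructs and items 2 to 5 run in the same order, so item 4 is evidently the one meant for ease of use. Its wording concerns an effect of the tool on a conversation, not how easy the tool is to operate.

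**Intention across the two waves**

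On Appendix D item 4 a score of 4 is printed as *Agree*. On Appendix E item 5 a score of 4 is printed as *I likely will*. The stems differ too: the first refers to patients thought to be at high risk, the second to occasions when the clinician has been alerted to increased risk. A difference between the two scores would mix a change in intention with a change in wording.

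**Where the items are used**

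Section M specifies no analysis of these items. Its 3-month analysis concerns stigma and the waiver and prescribing intentions of H1a to H1c. H1d takes Opioid Wizard use from CDS meta-data over 6 months (Sections H.a and H.b.iv), so it does not depend on a survey answer. Table 1 in Section L has no row for these items.

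**The case against.** The strongest reply is that nothing planned is broken. Section H.c.v fixes no scale, so the printed labels contradict no stated rule. Appendix D item 4 still gives an ordered 1-5 response, presented identically to both arms, and many respondents will read the top label as very likely. An arm comparison at that survey therefore remains possible. Section H.c.v says the initial questions are replaced at 3 months, and no change score is specified, so no planned comparison is lost. Appendix E item 4 sits where ease of use should be, and the documents do not define ease of use so narrowly as to exclude it outright. All of this stands, and it limits the point to interpretation and labelling.

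The reply does not remove two facts. The labels of Appendix D item 4 do not answer its question. And no 3-month item asks directly whether the tool is easy to use, although Section H.c.v names "Opioid Wizard ease of use, and intention to use Opioid Wizard in the future".

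A reader might go further and infer that these outcomes cannot be measured, or that ease of use is not collected at all. The documents do not support that: both constructs have an item in place, one badly labelled and one off target. A reader might also infer a loss of power. The documents give neither a reliability nor a planned effect for these items, and the detectable effects in Table 1 belong to other outcomes, so no such loss can be derived.

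**Conclusion.** The survey is wrong as written on two items, and the point is minor. Appendix D item 4 yields responses that are hard to interpret, though the arms can still be compared on it. Because its labels differ from those of Appendix E item 5, the two intention items should not be read as one scale. Appendix E item 4 measures whether the tool helps in discussing treatment, and should not be reported as ease of use.

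No numerical size can be put on this. Its extent is two items within one of the listed secondary outcomes. The primary outcomes (stigma, intention to get waivered, intention to prescribe, and Opioid Wizard use from CDS meta-data) and all stated hypotheses are unaffected.

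The label mismatch can be read directly from the page and needs no assumption. The point on ease of use rests on taking the phrase in its ordinary sense, how easy the tool is to operate, since Section H.c.v does not define it.

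**What to change.** If the surveys can still be changed:

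- In Appendix D item 4, replace the agree-disagree labels with those of Appendix E item 5, from *I definitely will not* to *I definitely will*.
- In Appendix E, add one direct item on whether Opioid Wizard is easy to use, with agree-disagree labels. Place it with items 2 to 4, which only clinicians who have used the tool answer, and update the skip instruction if the numbering moves.

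If the surveys are already fielded (the documents do not say):

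- Report the two intention items as separate measures, each with its printed labels, and compute no change score.
- Rename the 3-month outcome in Section H.c.v to what Appendix E item 4 asks, namely whether the tool makes discussing treatment options easier.

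The first route costs a REDCap edit, a minor amendment and at most one extra item for clinicians. The second needs no new data, only a change of wording in Section H.c.v and in the report.

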#### **WAIVERS AND INTENTIONS**

- 5. Are you currently waivered to prescribe buprenorphine/Suboxone?
  - a. YES
  - b. NO

5a. [If NO] Do you intend to get waivered to prescribed buprenorphine in the next year?

I definitely will		•		
not	I likely will not	Unsure	I likely will	I definitely will
1	2	3	4	5

5b. If a patient with OUD requested buprenorphine in the next year and a waiver were no longer required, would you prescribe buprenorphine?

,	, , , , , , , , , , , , , , , , , , , ,	Jean presente e alprente primite :					
I definitely	I likely would			I definitely			
would not	not	Unsure	I likely would	would			
1	2	3	4	5			

5c. [If YES] What is your buprenorphine waiver patient limit?

- 30
- 100
- 275
- Don't know

6. How often do you treat patients with opioid use disorder?

	A few	times a	Once or twice	Once or twice	
Never	y.	ear	a month	a week	Daily
1		2	3	4	5

#### DIFFERENCE, DISDAIN, & BLAME SCALE

7. How similar or different do you think a person with opioid use disorder is compared to everyone else in the general population?

	0 0100 111 1110	gonorai	population	•				
								Not at
								all
Very								similar
similar to								to
others								others
1	2	3	4	5	6	7	8	9

8. How good or bad you think a person with opioid use disorder is compared to everyone else in the general population?

Very								Not at all
good								good
1	2	3	4	5	6	7	8	9

9. How responsible do you think people with opioid use disorder are for their illness?

Not at all responsible								Very responsible
1	2	3	4	5	6	7	8	9

10. How like or unlike do you think a person with opioid use disorder is compared to everyone else in the general population?

Very much like others		J						Not at all like others
1	2	3	4	5	6	7	8	9

11. How respected or disrespected do you think a person with opioid use disorder is compared to everyone else in the general population?

Very								Not at all
respected								respected
1	2	3	4	5	6	7	8	9

12. How blamed do you think are people with opioid use disorder for their illness?

Not at all blamed				•				Very blamed
1	2	3	4	5	6	7	8	9

13. How comparable or not comparable do you think a person with opioid use disorder is compared to everyone else in the general population?

Not at all								Very
comparable								comparable
to others								to others
1	2	3	4	5	6	7	8	9

14. How favorable or unfavorable do you think a person with opioid use disorder is compared to everyone else in the general population?

Not at favorab								Very favorable
1	2	3	4	5	6	7	8	9

15. How much do people with opioid use disorder cause their illness?

								Did
Did								not
cause								cause
their								their
illness								illness
1	2	3	4	5	6	7	8	9

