#### F. Allocation of interventions

- **a. Methods for randomisation and stratification.** PCCs in clinics randomized to Opioid Wizard (in 15 of the 30 clinics randomized in the parent study) will be randomized 1:1 to the stigma reduction or comparison training, stratified by clinic and waiver status. Randomization will be generated using SAS software.
- b. Methods for concealment of allocation. PCCs will be blind to their randomized MyLearning training assignment. The study statistician ([name]) will generate the randomization assignment, and a study team member will submit that list to HP MyLearning staff. Study team members capturing outcome data from surveys, Opioid Wizard, and Epic (including use rates, buprenorphine prescriptions) will also be blind to treatment assignment.

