# b. Primary Outcome Measures

- i. *OUD Stigma*. Stigma of people with OUD will be measured using the *Difference* and *Disdain* scales, which measure stigma of people with mental illness and SUDs. 11,12,42 This measure was chosen because people are more willing to state that people with a health condition are different from them than to endorse general stigmatizing beliefs, therefore reducing social desirability in stigma measurement. Three items measure difference (the extent to which a person with OUD is similar, like, or comparable to others) and three items measure disdain (people with OUD are not good, not respected, or not favorable compared to others). Items are scored on a 9-point agreement scale; some items are reverse-scored so that higher scores reflect greater difference and disdain. Evidence suggests that the scales demonstrate good internal consistency and are positively associated. In addition, three items will assess blame as a secondary outcome (e.g., How responsible do you think a person with opioid use disorder is for his or her condition?). 43,44
- ii. Intentions to get waivered to prescribe buprenorphine. Non-waivered PCCs will be asked to rate one question on their intentions to get waivered to prescribe buprenorphine: "How likely are you to get waivered to prescribe buprenorphine in the next year?" PCCs will rate their response on a five-point Likert-type scale ranging from 1 (I definitely will not) to 5 (I definitely will). Behavioral intentions are commonly used proxies for behavior in behavioral science research and were chosen as the primary outcome for H1b and H2a because of the time it may take for a PCC to complete the waiver training, which may not occur during the study observation period (6-months post training). Across a wide range of behaviors, moderate-large changes in behavioral intentions are associated with small-moderate changes in behavior.

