#### K. Data collection and management

a. Data collection and management. Recruitment data will be stored in a protected project folder on a secure network drive. Surveys will be collected using REDCap, a secure data management software that stores data on internal HealthPartners servers. PCCs will get a link to the survey immediately after completing the training and will be instructed to fill out the survey in order to receive compensation for their time. PCCs will directly answer survey questions within the REDCap platform. For the follow-up survey, PCCs will receive an email and reminders at the time they are due for their follow-up. The email will have a link to the survey and PCCs will be able to directly answer the questions in the REDCap platform. Survey data will be accessed by study staff to determine which PCCs are eligible for incentives.

Opioid Wizard use will be captured passively through the Opioid Wizard system, and prescriptions, referrals, and patient characteristics will be captured through the EHR. PCC Waiver status will be extracted from HealthPartners administrative data at the end of the study follow-up period. Data will be extracted by the study team and stored securely on the HealthPartners secure internal server. Patient data will be identified with a random unique identifier generated by the Wizard platform. The study programmer will use that information to pull data from the EHR. No MRNs or patient IDs will be retained in an analytic dataset.

- **b. Quality control.** Survey responses will be directly entered by participants into REDCap survey software. We will program REDCap to minimize non-viable or non-allowable responses (e.g., limiting age to integers between 18 and 100). Participants will only be allowed to choose one Likert-type response on scale items. In addition, participants will be prompted to complete items that do not have a response, but will be allowed to leave them blank if they choose to do so.
- c. Progress reports. During study recruitment phases (initial training and follow-up survey), we will use REDCap reports to generate study completion rates and to prompt reminders to complete the training and surveys. The team will review the reports to determine if other strategies (e.g., reaching out to clinic leadership) are needed to boost recruitment and retention.

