#### TREATMENT FUTILITY

22. In your opinion, how effective are available methods for treating opioid use disorder?

22: In your opinion, now encoure are available mounded for treating opicia dec discretif									
		Moderately							
Not at all effective	Somewhat effective	effective	Very effective						
1	2	3	4						

23. In your opinion, how likely are patients with opioid use disorder to comply with treatment recommendations?

Not at all likely	Somewhat likely	Moderately likely	Very likely
1	2	3	4

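### The survey appendices print a label naming disdain and blame directly above the primary stigma items; if REDCap displays it, it works against the stated reason for choosing that measure.

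*Combined protocol and SAP*

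**What the plan says.** Section H.b.i (OUD Stigma) makes the Difference and Disdain items a primary outcome. It explains the choice by respondents' greater readiness to call people with a condition different than to endorse stigmatising beliefs, "therefore reducing social desirability in stigma measurement". The same paragraph adds that "three items will assess blame as a secondary outcome".

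Appendix D (post-training survey) prints "DIFFERENCE, DISDAIN, & BLAME SCALE" above items 7 to 15. Appendix E (3-month survey) prints the same label above items 8 to 16.

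Section K.a describes delivery: "PCCs will directly answer survey questions within the REDCap platform". Neither it nor section H.a says whether section labels appear on the respondent's screen. The appendices also carry build notes, for example "5a. [If NO] Do you intend to get waivered to prescribed buprenorphine in the next year", so not all of their text is meant for respondents.

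Section H.c.iv names the two items on treatment effectiveness and compliance "PCC opioid treatment outcome expectancies" and lists them as secondary. Both appendices head those items "TREATMENT FUTILITY".

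**The concern.** A measure chosen because it is less open to socially desirable answering loses some of that advantage if its purpose is announced. The label puts two plainly negative words directly above items about how similar, good or respected a person with OUD is. A clinician who reads it may shade answers toward the low (less stigmatising) end of the 9-point scale.

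If that happens in both arms, scores can bunch near the floor and a real difference between trainings becomes harder to detect. The trial's data could not show this afterwards. Every respondent would have seen the same form, so bunching might be visible but its cause would not be. H1a is one of four primary outcomes. Stigma is also the predictor in H2a and H2b, so lost spread would affect Aim 2 as well.

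**Working it through.** **Which items are affected.** Matching Appendix D to section H.b.i:

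| Construct | Appendix D items | Appendix E items | Status |
|---|---|---|---|
| Difference (similar, like, comparable) | 7, 10, 13 | 8, 11, 14 | primary |
| Disdain (good, respected, favorable) | 8, 11, 14 | 9, 12, 15 | primary |
| Blame (responsible, blamed, cause) | 9, 12, 15 | 10, 13, 16 | secondary |

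Six of the nine items under the label are the primary measure. The blame items are interleaved with them, so all nine share the one label.

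**Rationale against layout.** Section H.b.i relies on indirect questioning. The layout names the constructs. The two conflict only if the label is displayed, and that is not stated. Typography does not settle it. In the text as read from the PDF, the experience and waiver headings (and the demographics heading in D) are bold and the construct headings are not, which may be only an artefact of reading.

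**What a common cue could do.** If the label moves everyone down equally and nobody reaches the end of the scale, the between-arm difference is unchanged. The loss arises if the low end compresses the difference relative to its spread. The documents give no figure for this, so the shrinkage below is assumed.

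Inputs: the detectable effects for H1a in Table 1 of section L, at 80% power and two-sided alpha 0.05 with equal arms: d = 0.47 for 146 PCCs and d = 0.42 for 180.

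Formula: power = P(|T| > t(0.975, N − 2)), where T is noncentral t with N − 2 degrees of freedom and noncentrality δ = d·√N / 2.

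Reproducing the plan first:
- N = 180: δ = 0.42 × 13.416 / 2 = 2.82, power 80%.
- N = 146: δ = 0.47 × 12.083 / 2 = 2.84, power 80.5%.

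Both agree with Table 1. The 112-PCC column is left out because its stated 0.49 does not reproduce two-sided (0.53 is obtained). That is a separate matter.

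With d multiplied by (1 − shrinkage):

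| Assumed shrinkage | N = 180: d, δ, power | N = 146: d, δ, power |
|---|---|---|
| 10% | 0.378, 2.54, 71% | 0.423, 2.56, 72% |
| 20% | 0.336, 2.25, 61% | 0.376, 2.27, 62% |
| 30% | 0.294, 1.97, 50% | 0.329, 1.99, 51% |

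Zero shrinkage is also compatible with the documents. The table shows what a given loss would cost, not what loss to expect.

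**The other heading.** The expectancy items come after the stigma items (22 and 23 in D, 23 and 24 in E), so their heading cannot cue H1a on a first pass through the form. They are secondary, and the rationale in H.b.i does not cover them. The word used could prime pessimism as easily as a favourable answer.

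**The case against.** The strongest reply is that the labels may never reach a respondent. The appendices mix item text with branching and skip notes. One heading refers to physicians although nurse practitioners and physician assistants are also eligible, which reads like an internal scale name. This stands: display is an open question, and the point is conditional on it.

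A second reply is that the items are transparent anyway. Asking how good or how respected a person is leaves little to guess, and H.b.i speaks of item content without promising that the construct is hidden. This also stands in part: the added effect of the label may be close to zero. It does not explain why a loaded label should be shown when a neutral one would do.

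A reader might go further and infer a false-positive risk for H1a. Only the stigma arm has just heard the narratives and language advice, so the label might act more strongly there. If it lowered that arm's scores by an extra 0.1 or 0.2 SD with no true effect, the chance of p < 0.05 would be 8% or 18% with 112 PCCs, 9% or 22% with 146, and 10% or 27% with 180. The arithmetic is right, but nothing in the documents supports an extra shift of that size. At 0.02 SD the figure is 5.1% to 5.2%, and at 0.05 SD 5.8% to 6.3%. Both arms answer the same form, and section F.b states that "PCCs will be blind to their randomized MyLearning training assignment". Blinding does not make the training content the same, so a differential effect cannot be excluded. Most of that demand, however, would come from the training itself, measured straight afterwards, and changing a label would not remove it.

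**Conclusion.** The point holds as a minor, conditional one. The label stands above the primary stigma items in both surveys, and displaying it would work against the plan's own reason for choosing the measure. The conclusion assumes that REDCap shows section labels as drawn and that clinicians react to the words. The first is not stated, and the second is a plausible inference that the documents do not test.

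The size is unknown. The main risk is compressed scores and lost sensitivity; the power figures above depend wholly on the assumed shrinkage. The documents do not support reading the label as a demonstrated source of bias in favour of the stigma training. Nor do they support treating the treatment-expectancy heading as a threat to the primary measure; that is a question of wording only. Opioid Wizard use, another primary outcome, is taken from system data and is untouched.

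**What to change.** Before fielding, state in section K.a or in the appendices whether section labels are displayed in REDCap. If they are, suppress the label above the stigma items in both forms or replace it with a neutral one such as *Your views about patients*. Do this identically in both arms and in Appendices D and E, and leave item wording, order and scoring unchanged.

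As a separate and lesser edit, give the treatment-expectancy items a neutral label in line with the term already used in section H.c.iv.

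The cost is a text edit in two forms, with no loss of data and no change to the scales. That holds only if the edit is made before the first response. If a survey is already in the field, keep that survey's form constant rather than mix versions, and report whether the labels were shown.
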